## 6.2. Incomplete and Missing Prior and Concomitant Medication Start Date

The following imputation rules will be followed, when the prior and concomitant medication start date is incomplete (e.g., only *year* is present, but *month* and *day* are missing) or completely missing:

- If *year* is missing (including the situation where the start date is completely missing), do not impute, and the start date will be treated as missing in the analysis. Medications with missing start date will be considered concomitant for the purpose of summary tables.
- If *year* is present, and *month* and *day* are missing, or *year* and *day* are present, and *month* is missing, set *month* and *day* to January 1st.
- If *year* and *month* are present, and *day* is missing, set *day* to the first day of *month*.

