8.1.4. Medication Review (Prior and Concomitant Medications)

The investigator or medically qualified designee should review the participant's prior medication use within 30 days. Medication that is required to be washed out prior to the study should also be recorded. All medication(s) currently taken by the participant, as well as all concomitant medication(s) taken during the study, should be recorded (see [Section 6.8](#)).

Additional information related to any medications taken for the treatment of PD and/or other treatments specific for tremor (eg, propranolol, primidone) since diagnosis should also be collected.

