#### **4.7.6. Prior and Concomitant Medications**

##### **Derivations and Definitions:**

Prior and concomitant medications will be coded to ATC level 4 and preferred drug name using WHO Drug Dictionary Version March 2024, and will be classified as follows:

Prior medication is defined as any medication started prior to the first dose of study treatment.

Concomitant medication is defined as any medication started prior to the first dose of study intervention and continued beyond the first dose of study treatment, or any medication started on or after the first dose of study treatment up to the last dose of study treatment.

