##### **Prior and Concomitant Medications Summaries:**

- Summary of prior medications (Safety Analysis Set, and FAS)
- Summary of concomitant medications (Safety Analysis Set, and FAS)
- Summary of concomitant PD medications (FAS)

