### 6.3. Incomplete and Missing Prior and Concomitant Medication End Date

The following imputation rules will be followed, when the prior and concomitant medication end date is incomplete (e.g., only *year* is present, but *month* and *day* are missing) or completely missing:

- If it is indicated that the medication is ongoing (i.e., “Yes” is checked for the question “Ongoing?” in the CRF), do not impute, since there should not be an end date for this medication.
- If *year* is missing (including the situation where the end date is completely missing), do not impute, and the end date will be treated as missing in the analysis.
- If *year* is present, and *month* and *day* are missing, or *year* and *day* are present, and *month* is missing, set *month* and *day* to December 31st.
- If *year* and *month* are present, and *day* is missing, set *day* to the last day of *month*.

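### SAP 6.2 counts a medication with no start year as concomitant even when its end date shows that it stopped before the first dose

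*SAP*

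**What the plan says.** SAP 4.7.6 defines two classes. For the first: "Prior medication is defined as any medication started prior to the first dose of study treatment". A drug begun before dosing is also concomitant if it is "any medication started prior to the first dose of study intervention and continued beyond the first dose of study treatment". A drug begun on or after the first dose, up to the last dose, is concomitant as well.

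SAP 6.2 deals with incomplete start dates. If the year is missing, the instruction is "do not impute, and the start date will be treated as missing in the analysis", followed by "Medications with missing start date will be considered concomitant for the purpose of summary tables". If the year is known, the missing parts are filled with the earliest possible date.

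SAP 6.3 deals with incomplete end dates. A partial end date is filled with the latest possible date. An ongoing drug is given no end date. For an end date without a year the instruction is "do not impute, and the end date will be treated as missing in the analysis".

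The SAP plans tables of prior and of concomitant medications (Safety Analysis Set and Full Analysis Set) and a table of concomitant PD medications (Full Analysis Set). It also plans listings of prior and of concomitant medications.

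Protocol 8.1.4 sets a 30-day look-back for prior medication in general and asks that washed-out drugs be recorded. It also asks for "Additional information related to any medications taken for the treatment of PD and/or other treatments specific for tremor", going back to diagnosis.

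**The concern.** The rule in 6.2 looks at one date only. When the start year is unknown, the end date may still settle the matter, and 6.2 does not consult it. The SAP then gives two answers for the same record: prior only by definition, concomitant by the missing-date rule.

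This trial could produce such records in two ways. PD and tremor treatments are asked about back to diagnosis, treatment-naïve patients are excluded, and inclusion criterion 5 foresees participants who tried PD drugs and stopped. Separately, exclusion criteria 23 to 25 require certain drugs to be discontinued before Baseline, and 8.1.4 asks for washed-out drugs to be recorded. Those drugs end before dosing by design.

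At stake is the accuracy of the tables that describe what participants were taking during treatment. A drug that nobody was taking would be counted there, and a correctly washed-out drug could look as if it had been continued.

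**Working it through.** The plan gives no figure to reproduce, so the check is a trace of SAP 6.2 and 6.3 against the 4.7.6 definitions for each combination of dates.

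| Case | Start date | End date | SAP 6.2/6.3 result | SAP 4.7.6 result | Agreement |
|---|---|---|---|---|---|
| A | Year missing | Known, or completed under 6.3, and before first dose | Concomitant | Prior only | No |
| B | Year missing | Ongoing, or after first dose | Concomitant | Concomitant | Yes |
| C | Year missing | Missing, not marked ongoing | Concomitant by default | Cannot be decided | Default is defensible |
| D | Year known, before the year of first dose | Before first dose | Start filled with earliest date; prior only | Prior only | Yes |

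**Case A.** A drug cannot end before it starts. If its end precedes the first dose, so does its start, and it meets the definition of prior. It did not continue past the first dose, so it fails the first route to concomitant status. It did not begin on or after the first dose, so it fails the second. It is therefore prior only, although the exact start is unknown. SAP 6.2 nevertheless counts it as concomitant.

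**Does 6.3 repair this?** No. It completes partial end dates but contains no instruction to return a drug that ended before dosing to prior-only status.

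**Is a 6.3-completed end date safe to use for an exception?** Yes, because 6.3 always moves the end as late as it can. An end known only by a year before the year of first dose becomes 31 December of that year, which still precedes dosing. An end known by month, in a month before the month of first dose, becomes the last day of that month, which also precedes dosing. An end known only by the year of first dose becomes 31 December of that year and so does not precede dosing; the drug stays concomitant. An exception based on the completed end date therefore removes only drugs that had certainly stopped.

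**Effect of the exception.** Case A moves to prior only. Cases B, C and D do not change.

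**Number of records affected.** This would be the number of participants (160 planned), times the stopped drugs recorded per participant, times the share of those with no start year and an end before dosing. The documents give neither of the last two quantities, so no count is offered.

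**The case against.** The strongest reply is that this is a conservative convention of small reach, and most of that reply stands. The convention is confined by its own words to summary tables. It enters no hypothesis test. When the end date is also unknown, counting the drug as concomitant is reasonable. The planned listing of concomitant medications lets a reader check individual records. None of this removes the contradiction in case A, where the end date is known and no conservative assumption is needed.

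Three stronger readings are tempting, and the documents do not support them.

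- *PD and tremor drugs stopped years ago will appear in the concomitant PD medication table.* Protocol 8.1.4 describes the since-diagnosis history as additional information. Neither document says that it is stored with the records behind the concomitant tables. The SAP does not define PD medication for this table, and inclusion criterion 5 names other tremor drugs such as propranolol separately. A stopped tremor drug held in the medication dataset would reach the general table, but not certainly the PD table.
- *The partial-start-date rule in 6.2 hides newly started drugs.* A drug begun after dosing and dated back to 1 January or the first of the month was still in use after the first dose, so it remains in the concomitant table; at most it is also counted as prior. Borrowing the adverse-event rule in SAP 6.1, which sets the start to the first-dose date, could make background PD drugs look new, although these must have been stable for at least 6 weeks before Screening.
- *Efficacy results are affected.* SAP 4.1.3 defines the intercurrent event by therapy used after the first dose, not by an imputed start date. Both the main and the supplemental approach apply treatment policy to additional therapy. The subgroups on PD medication change and prohibited medication use are not derived, by any stated rule, from the 6.2 convention.

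**Conclusion.** The concern holds as a minor error in descriptive tables. SAP 6.2 assigns concomitant status to any drug without a start year, and for a drug whose end date precedes the first dose this contradicts SAP 4.7.6. Such a drug is wrongly added to the general concomitant table. It is added to the concomitant PD table only if it is a PD drug and its record lies in the same dataset.

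The contradiction follows from the text alone and rests on no assumption. Its practical size is unknown: it depends on how often the start year is missing while an end before dosing is known, and on how the PD and tremor history is stored. The documents give no reason to expect a difference between arms. By its terms the rule does not affect the primary or key secondary analysis or the definition of intercurrent events.

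**What to change.** Add one exception to the sentence in SAP 6.2 that assigns concomitant status: 'unless the end date (after imputation under 6.3) is before the first dose of study treatment, in which case the medication is prior only.' Keep the concomitant default when the drug is ongoing, or when its end date is missing or falls on or after the first dose. Leave the partial-start-date rules as they are.

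The cost is one clause in the SAP and one line in the derivation of the medication flags. No new data are needed and no efficacy analysis changes.

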### 6.3. Incomplete and Missing Prior and Concomitant Medication End Date

The following imputation rules will be followed, when the prior and concomitant medication end date is incomplete (e.g., only *year* is present, but *month* and *day* are missing) or completely missing:

- If it is indicated that the medication is ongoing (i.e., “Yes” is checked for the question “Ongoing?” in the CRF), do not impute, since there should not be an end date for this medication.
- If *year* is missing (including the situation where the end date is completely missing), do not impute, and the end date will be treated as missing in the analysis.
- If *year* is present, and *month* and *day* are missing, or *year* and *day* are present, and *month* is missing, set *month* and *day* to December 31st.
- If *year* and *month* are present, and *day* is missing, set *day* to the last day of *month*.

